Per protocol, if a participant has FVIII replacement therapy around the day of a visit when FVIII activity measurement is scheduled, sample collection should be postponed at least 48 or 72 hours based on the FVIII product used (standard half-life or extended half-life respectively). For all FVIII activity summaries and analyses (including plots), any FVIII activity values measured within 96 hours after administering exogenous FVIII replacement therapy will be excluded as ineligible. In addition, FVIII activity assessments collected after a participant initiates or resumes a prophylaxis regimen will be excluded. If there are multiple observations for an individual in the same time window, for all FVIII activity analyses with the exception of geometric mean analyses, the average of an individual's FVIII activity values within the same time window will be used.

A listing of individual FVIII activity values for each participant will show assay used, observed values in collected units and in % normal units, visit name (including unscheduled visits), and the analysis visit (the visit to which the value has been slotted, either from the visit name, or derived by taking the integer part of relative day/7). Measurements within 96 hours after a FVIII replacement infusion or after a participant initiates or resumes a prophylaxis regimen, will be flagged in the listing and excluded from plots.

Group-level plots will be limited to protocol-defined study visits. If the derived week for an unscheduled assessment falls within the visit window of a protocol-defined visit, the unscheduled value will be displayed. Individual-level plots will use unslotted unscheduled

visit data points. Baseline for FVIII activity is defined as the latest valid measurement prior to IP infusion.

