### 3.1.2.1. Factor VIII Activity Geometric Mean

The primary endpoint of time course profile of FVIII activity will be determined for the participants in the cohort administered the dose level intended for Phase 3 (ie, Cohort 4,  $3 \times 10^{13}$  vg/kg). The geometric mean for each participant will be calculated and summarized with descriptive statistics across the cohort for each assay type, for each year of the study. The geometric mean is the antilog of the mean of the log-transformed values.

FVIII activity over time will be calculated for each participant as the geometric mean of all eligible FVIII activity measurements within each yearly window. The summary statistics across participants in each cohort, for each observation period, will include sample size, arithmetic mean, standard deviation, median, first quartile, third quartile, minimum, and maximum. Calculation of the geometric mean for Year 1 will use all available data points beginning with the week considered to be when ‘steady state’ (see [Section 3.3.5](#) for more detail) has been achieved (eg, Week 9), through Week 52 (Weeks up to 53 will be included per the Schedule of Activities [SoA]), including those measured at unscheduled visits, and those where multiple observations may fall into the same time window. If multiple eligible FVIII activity observations are collected on the same day, the average level of these observations will be used for the given day. FVIII activity measurements within 96 hours after a FVIII replacement infusion, as well as those collected after routine prophylaxis has been initiated or resumed, will be excluded.

The geometric mean of FVIII activity will be similarly calculated for each assay type in the following designated yearly time periods (allowing for the 1 month flexibility in the SoA visit schedule after the first year) as indicated below:

Time period	Geometric Mean Window
Week 54 through Week 108 (Week $104 \pm 4$ weeks)	FVIII Activity Year 2
Week 109 through Week 160 (Week $156 \pm 4$ weeks)	FVIII Activity Year 3
Week 161 through Week 212 (Week $208 \pm 4$ weeks)	FVIII Activity Year 4
Week 213 through End of Study (Week $260 \pm 4$ weeks)	FVIII Activity Year 5

If a participant has not yet been followed for the full interval or has missing data, then all available data will be included to calculate geometric mean despite the missed measurements.

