The number of days in the observation period will be calculated as (date of data cut [or conclusion date] – [date of IP infusion + 21 days] + 1), which will then be annualized within the AIR formula. All infusions during the observation time period for any purpose (to treat bleeding, for preventive purpose, perioperative, or if FVIII prophylaxis regimen is initiated or resumed) will be included in the calculation of AIR. If no FVIII replacement infusions are reported during an observation period, AIR will be reported as zero.

A within-participant absolute difference, as well as percent reduction from pre-IP infusion AIR, will be calculated and summarized for the pre-study infusion calculation method that includes FVIII replacement therapy for any reason.

The five yearly windows defined in [Section 5.2](#) will be used for this AIR analysis. An additional observation period is defined for the entire length of follow-up, >week 3 through Year 5.

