### 3.2.2. Annualized Bleeding Rate

The number of bleeding episodes (BEs) during 12 months prior to the Screening visit will be collected in the Hemophilia History eCRF directly and will be used as the pre-screening rate. This form does not distinguish between treated or untreated bleeding episodes, only “total” pre-screening rate will be available.

The post-IP treated ABR will be calculated as:

$$[(\text{number of BEs requiring FVIII treatment recorded for the participant starting 3 weeks after IP infusion}) / (\text{number of days in observation period for the participant})] * 365.25.$$

If a FVIII prophylaxis regimen is initiated or resumed for a participant, then the time period (beginning with the first day of prophylaxis initiation or resumption) will be excluded from the treated ABR. The bleeding events after prophylaxis initiation or resumption will be excluded and the time period while on prophylaxis regimen will be deducted from the observation period, as well.

For all participants, treated bleeds (and days for the denominator) will be counted beginning on Day 22, and will stop counting when (the first of) any of the following happen:

1. The subject initiates or resumes routine prophylaxis (first day of resumption will not be counted);
2. The subject completes or discontinues (this day will be counted if data were collected);
3. Data cut or freeze date (this day will be counted if data were collected).

The number of days in the observation period will be calculated as (date of day before start of prophylactic dosing [or date of data cut or conclusion date] – [date of IP infusion + 21 days] + 1) which will then be annualized within the treated ABR formula. If no treated

bleeding episodes are reported during an observation period, treated ABR will be reported as zero.

During the post-IP period, multiple concurrent BEs (eg, two or more BEs that occur on the same date and time but in different sites in a participant) will be recorded as one bleed for overall treated ABR, but as separate BEs for that participant for treated ABR by location type (one episode for each unique location type, if they are different). Both spontaneous and traumatic treated bleeds will be counted towards the derivation of overall treated bleeding rate. BEs associated with a surgical procedure (perioperative and/or during the surgical rehabilitation period) will not be included in the treated ABR calculation.

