### 6.2.3. EQ-5D-5L

EQ-5D-5L VAS score and Index score results and change from baseline will be summarized as continuous variables by visit, stratifying by dose level (cohort) and overall (across dose levels).

For EQ-5D-5L dimensions, summary will be provided with counts and percentages of scores in each dimension by visit.

Listings of EQ-5D-5L dimension scores, VAS score, and Index score data will be created.

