### **6.5.2. Study Conduct and Participant Disposition**

The number of screened participants will be summarized. For screen failures, the reason for screen failure will be summarized using counts and percentages. No stratification by dose level will be implemented for this analysis. Enrolled participants are those who have been screened, are not considered to be a screen failure, and who have been approved by the Medical Monitor. A participant will be considered to have completed the study if he has completed all phases of the study including the End-of-Study visit (Month 60).

The number of participants enrolled, completing the study, discontinuing from the study and the primary reason for discontinuation, and the number of deaths (if any), will be summarized (number and percentage of enrolled participants in each population used for analysis), stratifying by dose level and overall. The number of ongoing participants will be included for outputs provided prior to the final analysis.

Listings will be provided for participant disposition, along with reasons for exclusion or discontinuation. An additional participant-level listing will be provided, indicating each observation period (Year) that he entered, and his duration in that period, along with his total study duration, as of the date of data cut (or conclusion date).

Potentially important protocol deviations (corresponding to those reported as 'Major') will be presented in a data listing.

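### Yearly FVIII activity and treated-ABR summaries stop at prophylaxis, and no planned table says how many participants have resumed or when

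*SAP*

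**What the plan says.** **FVIII activity.** SAP 3.1.2 removes, from every summary, analysis and plot, any value within 96 hours of replacement product and any value after prophylaxis starts: "FVIII activity assessments collected after a participant initiates or resumes a prophylaxis regimen will be excluded". SAP 3.1.2.1 repeats this for the yearly geometric means, which are planned for Cohort 4 only: values near an infusion, "as well as those collected after routine prophylaxis has been initiated or resumed, will be excluded".

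**Treated ABR (SAP 3.2.2).** Counting of bleeds and days ends at the first of several events, one being: "The subject initiates or resumes routine prophylaxis (first day of resumption will not be counted". The same section says that "the time period while on prophylaxis regimen will be deducted from the observation period". It also has a zero rule: if no treated "bleeding episodes are reported during an observation period, treated ABR will be reported as zero".

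**Outputs that keep the participant.** In SAP 3.2.1, infusions for any purpose, "or if FVIII prophylaxis regimen is initiated or resumed) will be included in the calculation of AIR". In SAP 6.2.3, "EQ-5D-5L VAS score and Index score results and change from baseline will be summarized as continuous variables by visit", with no prophylaxis exclusion.

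**Accounting tables.** SAP 6.5.2 summarises "The number of participants enrolled, completing the study, discontinuing from the study and the primary reason for discontinuation", together with deaths. SAP 6.1.1 uses the number still followed at the start of each year as the AE denominator. SAP 3.1.2.1 shows the sample size for each FVIII window. Post-infusion FVIII therapy is listed, not tabulated (SAP 6.5.4).

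**The concern.** The FVIII time course is a primary objective, and Protocol 9.4.3 gives durability of effect as a reason for following participants through Years 2 to 5. Once a participant goes on prophylaxis and stays on it, he has no eligible FVIII value and no treated-ABR day in any later year. The late-year FVIII and treated-ABR tables therefore describe those still off prophylaxis, while AIR and EQ-5D-5L in the same report describe everyone in follow-up. A reader who compares Year 2 with Year 4 cannot tell from the tables how much of any change comes from a changed group of participants.

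Two features of treated ABR add to this. A participant who resumes early in a year contributes a short window with the same weight as a full year. A participant who resumed before the year began has no days at all, and the zero rule does not say what to do with him.

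**Working it through.** The documents give no figure to reproduce: no inference is planned, and no resumption rate is stated.

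**1. Which outputs carry the information.**

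| Output | After prophylaxis starts | Counts or times resumption? |
|---|---|---|
| FVIII by visit (SAP 6.1.2) | excluded | no |
| FVIII yearly geometric mean, Cohort 4 (6.1.2.1) | excluded | no; n per window only |
| Treated ABR by year (6.2.2) | bleeds and days stop | no |
| AIR by year (6.2.1) | kept, all purposes pooled | no |
| EQ-5D-5L by visit (6.2.3) | no exclusion written | no |
| Disposition (6.5.2) | study completion and discontinuation | no |
| AE tables by year (6.1.1) | number still followed | no |
| FVIII listing (3.1.2), ABR listing (6.2.2), therapy listings (6.5.4) | flagged or listed | case by case only |

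Follow-up minus FVIII n gives the number not contributing, but not why. Besides resumption, a participant can be absent through missed samples, through later dropout in that year, or because every sample fell within 96 hours of an infusion. After Week 52 the schedule guarantees two FVIII samples per yearly window (for example Months 18 and 24 in Year 2). This is a minimum, since Schedule of Activities footnote m allows more.

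**2. FVIII, illustration only.** Assumed inputs: lognormal levels with log SD s = 0.8 or 1.2, and a fraction p resumed. In the extreme case where all resumers rank lowest, the median of those left is percentile (1+p)/2 of everyone, so the ratio of medians is exp(s × z[(1+p)/2]).

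- p = 0.07: z = 0.088, ratio 1.07 to 1.11
- p = 0.20: z = 0.253, ratio 1.22 to 1.36
- p = 0.40: z = 0.524, ratio 1.52 to 1.88

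With an assumed latent correlation of 0.5 between level and resumption, simulation gives 1.05 to 1.08, 1.14 to 1.22 and 1.29 to 1.46. With no link the ratio is 1.00.

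**3. Treated ABR, part-year windows.** Assumed: five participants, true rate 2 per year, Poisson bleeds.

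*Precision.* Take three windows of 365 days and two of 30 days, fixed in advance. With Y = 365/365.25 and S = 30/365.25:

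- SD of the mean of participant ABRs = sqrt(3×2/Y + 2×2/S)/5 = sqrt(6.00 + 48.70)/5 = 1.48
- SD of the person-time rate = sqrt(2/(3Y + 2S)) = sqrt(2/3.16) = 0.80

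*Bias when stopping follows bleeding.* Let two of the five stop 30 days after a bleed if that falls within the year, and otherwise run the full 365 days. By simulation:

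- Stop after the second bleed: the two average 2.88, so the mean is (3×2.00 + 2×2.88)/5 = 2.35.
- Stop after the first bleed: the two average 3.70, so the mean is (3×2.00 + 2×3.70)/5 = 2.68.
- The pooled person-time rate averages 2.03 under either rule.

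**4. Windows wholly after resumption.** At-risk days are 0 and bleeds are 0, so the ABR formula is 0/0. If the zero rule is applied literally to k of n such windows, a mean of 2.0 becomes 2.0 × (n − k)/n. With n = 5 this is 1.6 for k = 1 and 1.2 for k = 2.

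**The case against.** The case for leaving the plan alone is fair in several respects.

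- *The exclusion is correct.* A reader might infer that resumers' FVIII values should go back in. They should not: those values reflect replacement product.
- *Much of the accounting exists.* A reader might infer that resumption is inseparable from dropout. That goes too far, because SAP 6.1.1 gives the number followed at the start of each year and SAP 3.1.2.1 gives n per FVIII window. The 96-hour rule empties a year only if it removes every sample in it. What is missing is one count and its timing.
- *The study is small and descriptive.* With about 20 participants in four cohorts, listings and cohort plots can be read person by person. A sustained resumer would also stand out in the AIR maximum, given the roughly three infusions a week cited in Protocol 2.2.1. This lowers the stakes, but AIR pools all purposes and does not count resumers. In a descriptive study the tables are the result.
- *The zero rule may never be applied that way.* The post-resumption period is excluded from treated ABR, so a window without days may be held to have no observation period. That is a sensible reading, but the text does not state it.
- *The FVIII ratios are assumed throughout.* This stands. They show direction and mechanism, not an expected size.

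**Conclusion.** The reporting gap is real: after prophylaxis starts, the FVIII and treated-ABR summaries continue without the participant, and no planned table counts or times resumption. This holds whatever causes resumption.

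A reader might go further and infer that the Year 2-5 FVIII summaries do overstate durability. The documents do not support that as a fact. They do not tie resumption to lost expression; the nearest wording, in Protocol 6.5, is that participants adjust replacement to their needs. The overstatement is conditional on such a link, and its size cannot be derived.

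For treated ABR, a reader might infer that the cut always flatters the result, or that short windows add only noise. Neither holds in general. If stopping follows bleeding, part-year windows push the mean of participant ABRs up, which is less favourable (2.35 to 2.68 against 2.0 under the assumed rules). Only zero-day windows scored as 0 pull it down, and that scoring is one literal reading of SAP 3.2.2.

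The change is worth making and modest in scale. It needs no new data.

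**What to change.** **(a) Show resumption.** Keep the exclusion. By year, show n contributing, n in follow-up, n (%) who have started or resumed prophylaxis, and time to resumption. Place this for Cohort 4 beside the FVIII geometric means, and by dose level beside the by-visit FVIII and treated-ABR tables. Add a labelled sensitivity summary of the Cohort 4 yearly FVIII median and quartiles, with resumers still in follow-up ranked lowest. State that the ranking is an assumption. Report any quantile that falls among resumers as 'on prophylaxis' rather than as a number; this affects the first quartile above about 25% resumed and the median above about 50%.

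**(b) Treated ABR.** In SAP 3.2.2, report zero only when the window has at-risk days, and otherwise 'not evaluable'. Show at-risk days and a pooled person-time rate for each window.

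**(c) Clarification only.** SAP 3.2.2 both deducts time spent on prophylaxis and stops counting for good. The two differ if prophylaxis later ends, so reconcile them. State whether the cut also applies to total ABR and to the proportion with no bleeds.

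**Cost.** SAP wording and one small extra table. Prophylaxis start is already needed to apply the existing cuts, and SAP 3.2 has sites record the prescribed regimen in the eCRF. Late-year figures may look less favourable.

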### 3.1.2.1. Factor VIII Activity Geometric Mean

The primary endpoint of time course profile of FVIII activity will be determined for the participants in the cohort administered the dose level intended for Phase 3 (ie, Cohort 4,  $3 \times 10^{13}$  vg/kg). The geometric mean for each participant will be calculated and summarized with descriptive statistics across the cohort for each assay type, for each year of the study. The geometric mean is the antilog of the mean of the log-transformed values.

FVIII activity over time will be calculated for each participant as the geometric mean of all eligible FVIII activity measurements within each yearly window. The summary statistics across participants in each cohort, for each observation period, will include sample size, arithmetic mean, standard deviation, median, first quartile, third quartile, minimum, and maximum. Calculation of the geometric mean for Year 1 will use all available data points beginning with the week considered to be when ‘steady state’ (see [Section 3.3.5](#) for more detail) has been achieved (eg, Week 9), through Week 52 (Weeks up to 53 will be included per the Schedule of Activities [SoA]), including those measured at unscheduled visits, and those where multiple observations may fall into the same time window. If multiple eligible FVIII activity observations are collected on the same day, the average level of these observations will be used for the given day. FVIII activity measurements within 96 hours after a FVIII replacement infusion, as well as those collected after routine prophylaxis has been initiated or resumed, will be excluded.

The geometric mean of FVIII activity will be similarly calculated for each assay type in the following designated yearly time periods (allowing for the 1 month flexibility in the SoA visit schedule after the first year) as indicated below:

Time period	Geometric Mean Window
Week 54 through Week 108 (Week $104 \pm 4$ weeks)	FVIII Activity Year 2
Week 109 through Week 160 (Week $156 \pm 4$ weeks)	FVIII Activity Year 3
Week 161 through Week 212 (Week $208 \pm 4$ weeks)	FVIII Activity Year 4
Week 213 through End of Study (Week $260 \pm 4$ weeks)	FVIII Activity Year 5

If a participant has not yet been followed for the full interval or has missing data, then all available data will be included to calculate geometric mean despite the missed measurements.

## 3.2. Secondary Endpoints

An e-Diary on a handheld device is to be provided to each participant at baseline, which is to be used until the end of study. The participants are required to enter any occurrence of bleeding episodes (including date, time, location, and etiology) and any exogenous FVIII replacement (including date, time, reason, and dose) required to treat the bleeds in the e-Diary throughout follow-up regardless of whether or not the participant has initiated or resumed prophylactic therapy. If a participant has to initiate or resume FVIII prophylaxis

treatment, prophylaxis FVIII infusion data will not have to be reported on the e-Diary after Month 24 but the prescribed FVIII replacement regimen will be recorded in the eCRF by the sites and used to derive infusion data. On-demand and preventative infusions will continue to be required to be reported on the e-Diary throughout follow-up.

The protocol recommends prophylaxis FVIII treatment for up to approximately 2 weeks post PF-07055480 infusion (and may be used longer than 2 weeks, per investigator discretion), to provide protection against bleeding while allowing sufficient time for PF-07055480 to start FVIII expression. Participants are then switched to on-demand regimen. The first 3 weeks following treatment with PF-07055480 will not be considered in the analysis of annualized infusion rate (AIR) and annualized bleeding rate (ABR), to exclude contributions from prior routine prophylaxis, which could have been continued during this period.

### 3.2.1. Annualized Infusion Rate

The FVIII Administration electronic case report form (eCRF) and e-Diary will be used to collect each participant's pre-IP infusion FVIII medication details (including reason for infusion) beginning 30 days prior to the Screening visit through the Baseline visit (eCRF), and from Baseline to just before the IP infusion (e-Diary).

For pre-IP infusion, the AIR will be calculated in two ways:

- $[(\text{number of FVIII replacement infusions for reasons other than prophylaxis prior to IP infusion}) / (\text{[date of IP infusion} - \text{date of screening}] + 30)] * 365.25$ .
- $[(\text{number of FVIII replacement infusions for any reason prior to IP infusion}) / (\text{[date of IP infusion} - \text{date of screening}] + 30)] * 365.25$ .

Reasons for FVIII replacement therapy other than prophylaxis will include selective prevention of bleeding, prophylaxis for invasive procedures, and bleeding. In case a frequency other than "Once" is selected, the number of FVIII infusions to be added to the numerator of the above will be calculated based on the frequency of FVIII infusions and duration of treatment. A frequency of once per day will be used for frequencies listed as burst, taper, and titrate.

For post-IP infusion, the annualized infusion rate will be assessed as  $[\text{number of FVIII replacement infusions starting at 3 weeks (ie, Day 22 post-IP infusion)} / \text{(number of days in the observation period for the participant in years)}]$ . If the participant discontinued from study before the end of the prespecified time period, the last date in the observation period will be the date of study discontinuation. For all participants, post-IP infusions (and days for the denominator) will be counted beginning on Day 22, and will stop counting when (the first of) any of the following things happen:

1. The subject completes or discontinues (this day will be counted if data were collected).
2. Data cut or freeze date (this day will be counted if data were collected).

The number of days in the observation period will be calculated as (date of data cut [or conclusion date] – [date of IP infusion + 21 days] + 1), which will then be annualized within the AIR formula. All infusions during the observation time period for any purpose (to treat bleeding, for preventive purpose, perioperative, or if FVIII prophylaxis regimen is initiated or resumed) will be included in the calculation of AIR. If no FVIII replacement infusions are reported during an observation period, AIR will be reported as zero.

A within-participant absolute difference, as well as percent reduction from pre-IP infusion AIR, will be calculated and summarized for the pre-study infusion calculation method that includes FVIII replacement therapy for any reason.

The five yearly windows defined in [Section 5.2](#) will be used for this AIR analysis. An additional observation period is defined for the entire length of follow-up, >week 3 through Year 5.

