##### 5.2.1.1. Yearly Windowing

The following windowing option may be used when each yearly observation period used for analysis will be 365 days. Any dates beyond 1460 days will also be included with Year 5 for analysis. Post-infusion AIR and ABR yearly windowing begins with 3 weeks after the IP infusion where day is calculated relative to the IP infusion date. Post-infusion AE yearly windowing begins on the IP infusion date.

Window name	Derivation
Year 1	Day 22 $\leq$ Year 1 $\leq$ Day 365
Year 2	Day 365 < Year 2 $\leq$ Day 730
Year 3	Day 730 < Year 3 $\leq$ Day 1095
Year 4	Day 1095 < Year 4 $\leq$ Day 1460
Year 5	Day 1460 < Year 5

Further details of windowing will be described separately for each endpoint in [Section 2.1](#), as applicable.

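### The written day count for AIR and treated ABR covers only the whole follow-up; no denominator is stated for the five yearly windows in which the rates are reported

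*SAP*

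**What the plan says.** **AIR (SAP 3.2.1).** The day count is given once: "observation period will be calculated as (date of data cut [or conclusion date] – [date of IP infusion + 21 days] + 1"). The counting rule says the same for all participants, covering events "and days for the denominator) will be counted beginning on Day 22, and will stop counting when (the first of) any of the following things" occur. The two listed stops are completion or discontinuation, and the data cut or freeze. The end of a window is not among them.

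**Treated ABR (SAP 3.2.2).** The formula has the same start, and its end is the "date of day before start of prophylactic dosing [or date of data cut or conclusion date"]. The stop list adds prophylaxis to the two AIR stops, again with no window end. If no treated bleeds are reported in an observation period, treated ABR is set to zero.

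**Windows.** Section 3.2.1 then says that five windows, one per year, "will be used for this AIR analysis. An additional observation period is defined for the entire length of follow-up". Section 3.2.2 does likewise for treated and total ABR, and Sections 6.2.1 and 6.2.2 summarize by these intervals. Section 5.2.1.1 tabulates the day limits of each year and describes the option as one "when each yearly observation period used for analysis will be 365 days".

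**Interim analysis (SAP 7.2).** A separate observation-period formula starts at the infusion date and not 21 days later.

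**The concern.** The SAP has six observation periods (five years and the whole follow-up), but the day count written for each rate fits only the last of them. For Years 2 to 5 its start is too early. For any window that closes before the data cut or study conclusion, its end is too late. The cross-references do not fill the gap: Section 5.2.1.1 sends the reader to Section 2.1 for further windowing detail, and Section 2.1 holds only the objectives and endpoints.

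Yearly AIR and ABR are how the secondary clinical endpoint is followed over time, and Protocol 9.4.3 gives durability of effect as a reason for following participants in Years 2 to 5. AIR also feeds the difference and percent reduction from the pre-infusion rate. The analysis is purely descriptive (SAP 5.1), so these rates are themselves the result. Two programmers working from this text could produce different yearly figures.

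**Working it through.** **Inputs.** Relative Day 1 is the infusion date (SAP 5), so infusion + 21 days is Day 22. Window limits come from the SAP 5.2.1.1 table. Planned follow-up is 60 months (SAP 2.2); a last day of 1826 is assumed. Four events per window is an illustration, not a study figure. Rate = events × 365.25 / days.

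**Step 1: the stated 365 days against the table.**
- Year 1: 365 − 22 + 1 = 344
- Year 2: 730 − 366 + 1 = 365
- Year 3: 1095 − 731 + 1 = 365
- Year 4: 1460 − 1096 + 1 = 365
- Year 5 (open-ended): 1826 − 1461 + 1 = 366. At Day 1856, about one month later, it is 1856 − 1461 + 1 = 396.

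The stated 365 is reproduced for Years 2 to 4 only.

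**Step 2: the written formula.** Days = last day − 22 + 1.
- Last day 730: 709
- Last day 1095: 1074
- Last day 1826: 1805

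These are whole-follow-up lengths and match no yearly window.

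**Step 3: yearly rates under each reading (last day 1826, 4 events per window).**

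| Reading | Year 1 | Years 2–4 | Year 5 |
|---|---|---|---|
| Events and days both within the window | 4 × 365.25/344 = 4.25 | 4 × 365.25/365 = 4.00 | 4 × 365.25/366 = 3.99 |
| Events and days both from Day 22 to the end | 20 × 365.25/1805 = 4.05 | 4.05 | 4.05 |
| Events within the window, days from the written formula | 4 × 365.25/1805 = 0.81 | 0.81 | 0.81 |

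In the second row every year repeats the overall rate, so change over time cannot be seen. In the third row the understatement is the ratio of the denominators:
- Last day 1826: 1805/344 = 5.25, 1805/365 = 4.95, 1805/366 = 4.93
- Cut at Day 1095: 1074/344 = 3.12, 1074/365 = 2.94
- Cut at Day 730: 709/344 = 2.06, 709/365 = 1.94

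**Step 4: a flat 365 days for Year 1.** 344/365 = 0.942, so Year 1 would be 5.8% too low (4.00 instead of 4.25).

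**Step 5: treated ABR with prophylaxis from Day 901 (illustration).** The last eligible day is 900, and the written formula gives 900 − 22 + 1 = 879 days. Four Year 2 bleeds give 4 × 365.25/879 = 1.66 instead of 4.00. Year 3 has 900 − 731 + 1 = 170 eligible days. Years 4 and 5 have none, and the SAP does not say whether the zero rule applies to such a window.

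**Step 6: the interim formula.** For a participant cut at Day 365, Section 7.2 gives 365 days and Section 3.2.1 gives 344; 365/344 = 1.061, a 6.1% larger denominator.

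**The case against.** The strongest reply is that the SAP plainly means each year to be its own observation period, and much of that stands:
- Section 5.2.1.1 gives explicit day limits and starts AIR and ABR windowing three weeks after infusion.
- Section 3.2.1 says "If the participant discontinued from study before the end of the prespecified time period, the last date in the observation period will be" the discontinuation date, which implies that the period otherwise ends with the prespecified period.
- The whole follow-up is called an additional period.
- Section 6.5.2 plans a listing of each year a participant entered and his duration in it, separately from total duration.

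A careful programmer would probably window both events and days.

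Some stronger readings are tempting but unsupported. A reader might infer that the plan divides one year's events by the whole follow-up. No section says so: the counting rules take events and days over the same span, and the 5-fold figure needs windowed events over an unwindowed denominator. Nor is every yearly rate necessarily far too low, since the size depends on the reading and the length of follow-up. A reader might also think that someone who leaves mid-year is given 365 days, but the discontinuation rules in 3.2.1 and 3.2.2 exclude that. Nor is there only one formula: treated ABR has its own, and 7.2 has another.

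The 365-day statement can be read as a nominal width in an optional rule, and the planned listings of bleeds, infusions and rates would let a reader trace an error. These points limit the consequence. They do not supply the denominator: intent has to be pieced together from other sections, against a written formula and stop lists that say otherwise.

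**Conclusion.** The point holds as an omission with a conflict in the text. The AIR and treated-ABR day counts are written for the whole follow-up only, while the rates are reported by year. The per-window intention is visible but never stated as a calculation. Taken literally, yearly rates either all equal the overall rate or are too low by about 2-fold at a 2-year cut and about 5-fold at 60 months. Separately, the 365-day wording contradicts the 344-day Year 1 window (5.8% if applied) and does not describe open-ended Year 5, and the interim formula conflicts with the Day 22 start (6.1% at one year). The fold figures rest on the assumed last days and on reading only the events as windowed; the rates rest on illustrative event counts. The documents do not show that any analysis was run this way.

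**What to change.** 1. In SAP 3.2.1 and 3.2.2, state that for each window days = min(window end, completion or discontinuation, data cut, and for treated ABR the day before prophylaxis) − max(window start, Day 22) + 1, with events counted over exactly those days. For a Day 1826 completer without prophylaxis this gives 344, 365, 365, 365 and 366 days.
2. State that a window with no eligible days is not evaluable, and limit the zero rule to windows with at least one eligible day.
3. Keep the present formulas for the whole-follow-up period only.
4. In 5.2.1.1, replace the 365-day statement by actual days in the window: at most 344 for Year 1 AIR and ABR, at most 365 for Years 2 to 4, and actual days for Year 5. Correct the cross-reference to Section 2.1.
5. Reconcile the interim formula in 7.2 with the Day 22 start for AIR and ABR.
6. Say whether total ABR also stops at prophylaxis. The text sets that exclusion for treated ABR, and this change does not settle it for total ABR.

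The cost is SAP wording and one programming specification. No new data are needed.
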